12 CORRELATIVE STUDIES

Archived tumor samples or samples from newly obtained tumor tissue will be collected prior to baseline and will be used to confirm mutation status retrospectively in all patients and to assess expression of specific mutations and biomarkers in consenting patients.

Blood samples will be collected for biomarker analysis at Cycle 1 Day 1, Cycle 2 Day 1, and end of treatment. Whole blood samples will be collected in two 10 mL cell-free DNA BCT (Streck) blood collection tubes and two 10 mL BD Vacutainer EDTA tubes with total volume of collection no more than 40 mL. Tumor tissue will be collected for retrospective concordance mutation testing and correlation with biomarkers.

13 ADVERSE EVENT REPORTING REQUIREMENTS

13.1 PURPOSE

AE data collection and reporting, which are required as part of every clinical trial, are done to ensure the safety of patients enrolled in the studies as well as those who will enroll in future studies using similar agents. AE are reported in a routine manner at scheduled times during a trial. Additionally, certain AEs must be reported in an expedited manner to allow for more timely monitoring of patient safety and care. The following guidelines prescribe routine and expedited AEs reporting for this protocol.

Throughout the study, the Investigator will be required to provide appropriate information concerning any findings that suggest significant hazards, contraindications, side effects, or precautions pertinent to the safety of the drug under investigation.

Note: All deaths on study require both routine and expedited reporting regardless of causality. Attribution to treatment or other cause must be provided.

13.2 DEFINITION OF ADVERSE EVENT

An AE is defined as any illness, sign or symptom which has appeared or worsened during the course of the study, regardless of causal relationship to the drug under study, experienced by a patient.

All adverse events should be recorded and described in the adverse event database in REDCap. Adverse events also include Grade 3 or 4 abnormal laboratory test results that were not noted in the Screening Phase.

Pre-existing diseases or conditions will not be considered AEs unless there is an increase in the frequency, duration or severity, or a change in the quality, of the disease or condition. Only grade 3 or 4 abnormal lab values that were not noted during the Screening Phase should be recorded; however, any clinical consequences of the abnormality, regardless of grade should be reported as AEs. Hospitalization for elective surgery or routine clinical procedures that are not the result of an AE (e.g., surgical insertion of central line) need not be considered AEs and should not be recorded as an AE. Progression of cancer also will not be considered an AE.

Death should only be entered as the outcome for an AE when the patient's death is at least probably related to the AE (Note: the causal relationship of the AE to the test article is not to be considered in making this decision). If more than 1 AE is possibly related to the patient's death, the outcome of death should be indicated for each such AE.

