2 OBJECTIVES AND ENDPOINTS

2.1 PRIMARY OBJECTIVE

Objectives	Endpoints
To evaluate the RP2D, safety, and tolerability of tarloxotinib in combination with sotorasib in patients with KRAS G12C mutated advanced non-small cell lung cancer (NSCLC).	Dose-limiting toxicities, treatment-emergent adverse events, treatment-related adverse events, clinically significant changes in vital signs, electrocardiograms, laboratory tests
To evaluate the tumor objective response rate (ORR) assessed by RECIST 1.1 criteria of the combination of tarloxotinib with sotorasib	Objective response (OR = CR+PR) measured by CT and assessed per RECIST 1.1. Complete response (CR) and Partial response (PR) require confirmatory CT repeat assessment at least 4 weeks after the first detection of response

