6.2 DEFINITION OF DOSE-LIMITING TOXICITY (DLT)

Toxicities will be graded according to the NCI Common Toxicity Criteria scale version 5.0. If multiple toxicities are seen, the presence of DLT should be based on the most severe toxicity grade experienced. DLT will be defined as any of the following events occurring during treatment with study drugs and is deemed possibly, probably or definitely attributable to the study drugs:

- Any Grade 3 or 4 thrombocytopenia, anemia and/or neutropenia.
- Any other non-hematologic Grade 3 or 4 toxicity that is clinically significant, excluding alopecia.
- Any grade 3 nausea, vomiting or diarrhea that persists > 72 hours despite the use of maximal medical intervention and/or prophylaxis as indicated by good clinical practice and the judgment of the investigator.
- Any grade 4 vomiting or diarrhea regardless of duration.
- Failure to recover from toxicities to be eligible for re-treatment within 4 weeks.
- Any death not clearly due to the underlying disease or extraneous causes, and for any toxicity requiring permanent discontinuation of study drug(s).
- Hy's law, defined as: AST or ALT > 3 x the upper limit of normal (ULN) with concurrent increase in total bilirubin > 2 x ULN without evidence of cholestasis or alternative explanations, (e.g., viral hepatitis, disease progression in the liver, etc.)
- Neutropenic fever

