6.5.6 Treatment Guidelines for Other Non-Hematologic Toxicity

The table below provides treatment guidelines for treating tarloxitinib non-hematologic toxicities other than QT prolongation and infusion-related reactions.

Toxicity (CTCAE v5.0)	Details	Hold Dose	Dose Levels After Recovery to \leq Grade 2 or Baseline
Grade 2	Intolerable skin toxicity or diarrhea	Hold dose until resolution to Grade 0 or 1 or Grade 2 tolerable	If symptoms are intolerable, recurrent, or not controlled by supportive care, hold dose until symptoms improve and reduce to next lower dose level
Grade 2	ALT or AST $> 3 \times$ ULN	Hold dose until resolution to $<$ Grade 2 or baseline	150 mg/m ² (no reduction)
	ALT or AST $> 3 \times$ ULN (Grade 2) AND a total bilirubin $\geq 2 \times$ ULN (patients without liver metastasis)**	Treatment to be discontinued	Not applicable
Grade 3	Nausea and vomiting*	Hold dose until resolution to Grade 0 or 1 or Grade 2 tolerable	120 mg/m ² ; if recurs, then second reduction to 75 mg/m ²
Grade 4	Pulmonary embolism that is adequately treated	Hold dose until resolution to Grade 0 or 1	120 mg/m ² ; if recurs, then second reduction to 75 mg/m ²
Grade 4	All other life-threatening conditions	Treatment to be discontinued	Not applicable

ALT = alanine aminotransferase; ASP = aspartate aminotransferase; CTCAE = Common Terminology Criteria for Adverse Events; ULN = upper limit of normal

* May hold or reduce if nausea/vomiting continues despite optimized anti-emetic treatment

** Tarloxitinib-related toxicity meeting the definition of Hy's Law, tarloxitinib will be discontinued permanently

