7.1.8 Potassium Supplementation

Serum electrolytes (including potassium) will be checked prior to each tarloxotinib infusion.

- Tarloxotinib will not be administered if the serum potassium level is < 3.5 mEq/L.
- Patients with a serum potassium of < 3.5 mEq/L will receive potassium replacement per institutional policy (IV and/or oral) and have the scheduled tarloxotinib infusion delayed at least 24 hours and potassium levels rechecked within 1 hour prior to the rescheduled infusion.

All patients who present with a serum potassium level of ≥ 3.5 mEq/L will be given potassium supplementation prior to tarloxotinib infusion based on pre-infusion serum potassium result:

Potassium Supplementation Guidelines Pre-infusion	
Serum Potassium (mEq/L)	Potassium Supplementation Strategy
< 3.5	
• Hold tarloxitinib• Administer potassium replacement per institutional policy (IV and/or PO)• Delay the scheduled tarloxitinib infusion delayed at least 24 hours and potassium levels rechecked within 1 hour prior to the rescheduled infusion
3.5 to 4.0	
• All patients will be supplemented daily with 20 mEq of potassium (IV or PO).
> 4.0	
• Administer potassium replacement per institutional policy (IV and/or PO)

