11.2.4 SAFETY ANALYSES

All patients in the safety analysis set will be evaluated for safety and toxicity. Adverse events, SAEs and TEAEs will be summarized by System Organ Class (SOC) and by decreasing frequency of Preferred Term within SOC. Safety analyses will include the following summaries:

- AEs, including severity and possible relationship to study drug
- SAEs, including possible relationship to study drug
- AEs leading to dose adjustments
- DLTs and DLT-E events
- Discontinuations from study treatment due to AEs or death
- Treatment-emergent abnormal changes in laboratory values
- Treatment-emergent abnormal changes in vital signs and ECGs

AEs should be reported for 28 days after the last dose of tarloxotinib and/or sotorasib.

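### Section 13.2 records laboratory AEs only at Grade 3 or 4, so asymptomatic lower-grade values that hold or stop treatment have no AE to feed the AE-based summaries in 11.2.4

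*Combined protocol and SAP*

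**What the plan says.** Section 13.2 of the protocol first widens the AE definition: "Adverse events also include Grade 3 or 4 abnormal laboratory test results that were not noted in the Screening Phase". It then narrows what sites enter: "Only grade 3 or 4 abnormal lab values that were not noted during the Screening Phase should be recorded". The one exception is that "any clinical consequences of the abnormality, regardless of grade should be reported as AEs". That clause covers what the abnormal value causes, not the value itself.

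Elsewhere the protocol acts on laboratory values without asking for Grade 3:

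- Section 6.5.6 places ALT or AST above 3 × ULN in a Grade 2 row and holds tarloxotinib. A further row, "ULN (Grade 2) AND a total bilirubin" at or above 2 × ULN, leads to discontinuation in patients without liver metastasis.
- Section 6.2 makes Hy's law a DLT, defined by "AST or ALT > 3 x the upper limit of normal (ULN) with concurrent increase in total bilirubin" to more than 2 × ULN. Section 7.2.8 stops sotorasib permanently on the same multiples.
- Section 7.1.8 states "Tarloxotinib will not be administered if the serum potassium level is < 3.5 mEq/L". Section 6.5 requires magnesium and calcium to be normal before each infusion unless the Principal Investigator approves an exception.

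The endpoint cell in section 2.1 begins "Dose-limiting toxicities, treatment-emergent adverse events, treatment-related adverse events" and goes on to include clinically significant laboratory changes. Section 11.2.4 plans a summary of "AEs leading to dose adjustments" and one of treatment discontinuations attributed to AEs or death. It also plans separate summaries of DLTs and DLT-equivalents and of laboratory changes.

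**The concern.** The threshold for recording a laboratory AE is higher than the threshold for acting on the same value. Suppose a patient without symptoms has a transaminase that the protocol calls Grade 2 and misses a tarloxotinib dose because of it. Under 13.2 the site is told not to enter the value as an AE. Severity, action taken and relationship to study drug are fields of the AE form (13.6), so without an AE none of the three has a stated place to be recorded.

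At stake is how complete the AE-based part of the safety report will be. TEAEs and treatment-related AEs belong to the primary safety endpoint. The two lines in 11.2.4 that connect AEs to dose changes and to stopping are what a reader would consult to judge tolerability. Both would leave out laboratory-driven actions below Grade 3, and the omission runs in one direction, towards a better-looking profile.

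**Working it through.** The protocol states no figure on this point, so the check sets each laboratory trigger against the recording rule for a patient with no symptoms.

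| Section | Trigger | Grade given in the protocol | Action | AE entered under 13.2? |
|---|---|---|---|---|
| 6.5.6 | ALT/AST above 3 × ULN | Grade 2 | Tarloxotinib held | No |
| 6.5.6 | Same, plus bilirubin at or above 2 × ULN, no liver metastasis | Grade 2 for ALT/AST; none for bilirubin | Treatment discontinued | Not unless a component reaches Grade 3 |
| 6.2 | Hy's law (bilirubin above 2 × ULN) | None required | DLT | Not unless a component reaches Grade 3 |
| 7.2.8 | Same multiples as 6.2 | None required | Sotorasib stopped | Not unless a component reaches Grade 3 |
| 7.1.8 | Potassium below 3.5 mEq/L | None | Infusion delayed | Not unless Grade 3 |
| 6.5 | Magnesium or calcium out of range | None | Pre-infusion criterion not met | Not unless Grade 3 |

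The transaminase limb rests on the protocol's own Grade 2 label. That the bilirubin and electrolyte values lie below Grade 3 is an assumption, because the documents give no grades for them. Section 7.2.8 also holds sotorasib for Grade 2 transaminases with symptoms. There the symptoms would be recorded under the clinical-consequences clause, so that case is partly covered.

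Next, where each event would still be visible:

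1. Hy's law: under DLTs and DLT-equivalents (11.2.4).
2. The values: in the laboratory summary (11.2.4), which carries no Grade 3 threshold.
3. Omitted, reduced or delayed doses: in the exposure counts of 11.2.1.4, whatever the cause.
4. Stopping: the primary reason is recorded (9.3) and reported in disposition (11.2.1.1).
5. The reason for a schedule change: on the eCRF (7.1.4), with no summary by reason planned.

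None of these five ties the laboratory value to the dose action together with its severity and attribution. The outputs that would do so are built from AEs, and for these events there is no AE.

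On scale, if the 11.2.4 lines are reported as patients, each patient whose only dose-changing event is such a value lowers the rate in a 12-patient expansion cohort by 1/12 = 0.083, about 8 percentage points. How many such patients to expect cannot be derived from the documents.

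**The case against.** The strongest reply is that little is lost. Hy's law is a named DLT, and 6.2 requires a judgement of attribution before anything counts as one. Section 6.2 also makes any toxicity that forces permanent discontinuation a DLT. Laboratory changes are themselves a primary safety endpoint (2.1, 10.3). A low potassium delays the infusion by at least 24 hours, which can fall inside the ±1 day window of 7.1.4, and a magnesium or calcium exception can be approved. Whether every brief electrolyte delay deserves an AE is open to argument.

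Most of this stands and limits the point. It does not supply the missing link between cause, action and attribution, and the documents describe no separate DLT form to hold that judgement.

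It could also be said that a hold is itself a clinical consequence. Section 13.2 does not say so. A hold is a protocol action, not an illness, sign or symptom. If that reading was intended, sites could apply it differently and the text still needs a sentence.

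Three stronger readings are tempting and are not supported:

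- A reader might infer that Hy's-law cases vanish, or that the 3+3 or DLT-equivalent monitoring would miscount. Both rules use DLTs, which are reported separately, and nothing shows that a decision would change.
- A reader might infer that every dose-adjustment summary is affected. Section 11.2.1.4 counts dose changes regardless of cause; only the AE-based lines are affected.
- A reader might size the gap from the any-grade and high-grade columns in 3.1.7. Those are monotherapy rates, and the difference includes Grade 1 events that trigger nothing. Anemia of any grade requires no tarloxotinib modification (6.5.2).

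**Conclusion.** The point holds as an inconsistency between the recording rule and the dose rules. Followed as written, 13.2 leaves asymptomatic laboratory-driven holds and stops below Grade 3 without an AE. The two AE-based lines in 11.2.4, and the TEAE and treatment-related AE counts, would then be incomplete and slightly too favourable.

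The case is firmest for the Grade 2 transaminase hold. It is weaker for bilirubin and electrolytes, whose grades are assumed. The conclusion also assumes that sites follow 13.2 literally and that the value produces no symptom or other clinical consequence. It is a correctable recording gap with partial back-up elsewhere, not a threat to dose selection or to the monitoring rule.

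Separately, the bilirubin cut-off and population differ between 6.5.6 (at or above 2 × ULN, patients without liver metastasis) and 6.2 and 7.2.8 (above 2 × ULN, no such limit). These passages must be reconciled.

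**What to change.** Keep the Grade 3-4 rule in 13.2 and add one sentence: *A laboratory abnormality of any grade is also recorded as an AE if it meets a DLT criterion or leads to a hold, delay, omission, reduction or discontinuation of either study drug.* Add an eCRF check that asks for a linked AE whenever a dose change is attributed to a laboratory value.

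This changes recording only. It alters no dose, threshold or clinical rule and needs no extra blood test. The cost is the sentence, the check, a few more AE entries and a slightly less favourable AE table. It does not make any-grade laboratory AE rates complete, because lower-grade values that trigger nothing would still go unrecorded as AEs.

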13.3 DEFINITION OF SERIOUS ADVERSE EVENT

An SAE is defined by regulatory agencies as one that suggests a significant hazard or side effect, regardless of the investigator or sponsor's opinion on the relationship to investigational product. This includes, but may not be limited events that result in the following outcomes:

- Death
- Life-threatening. Patient was at substantial risk of dying at the time of the event or use or continued use of the medical product may have resulted in the death of the patient.
- Hospitalization (initial or prolonged). Report hospital admissions or prolongation of hospitalization. Emergency room visits that do not result in admission should be evaluated for one of the other serious outcomes.
- Disability or Permanent Damage. Report is the adverse event resulted in a substantial disruption of a person's ability to conduct normal life functions.
- Congenital anomaly/birth defect. Report if it is suspected that the exposure to the medical product prior to conception or during pregnancy may have resulted in an adverse outcome for the child.
- Other Serious or important medical events. If the event does not fit other outcomes, but may jeopardize the patient and may require intervention to prevent one of the other outcomes.

13.4 DEFINITION OF SEVERITY

Adverse events will be graded according to the revised NCI Common Toxicity Criteria. If toxicities are not defined by the NCI Common Toxicity Criteria v. 4.0, the intensity of each adverse event should be graded as outlined below:

GRADE 1	MILD: Sign or symptom noticeable, but does not interfere with normal daily activities.
GRADE 2	MODERATE: Sign or symptom sufficient to interfere with normal daily activities.
GRADE 3	SEVERE: Sign or symptom is incapacitating, with inability to perform daily activities.
GRADE 4	LIFE-THREATENING: sign or symptom poses immediate risk of death to this patient.

13.5 DEFINITION OF RELATIONSHIP TO STUDY DRUG

The categories for classifying the Investigator's opinion regarding the relationship of an AE to the study drug are listed below.

Definitely related:	An adverse event occurring in a plausible time relationship to drug administration, and which cannot be explained by concurrent disease or other drugs or chemicals. The response to withdrawal of the drug should be clinically plausible. The event must be definite pharmacologically or phenomenologically, using a satisfactory rechallenge procedure if necessary and feasible.
---------------------	---

Possibly related:	An adverse event with a reasonable time sequence to administration of the drug, but which could also be explained by concurrent disease or other drugs or chemicals. Information on drug withdrawal may be lacking or unclear.
Not related:	An adverse event with a temporal relationship to drug administration which makes a causal relationship improbable, and in which other drugs, chemicals or underlying diseases provide plausible explanations.

13.6 DOCUMENTATION OF ADVERSE EVENTS

The Investigator will monitor and/or ask about or evaluate AEs using non leading questions at each visit or evaluation. The occurrence of all AEs will be documented in the CRF with the following information, where appropriate:

- AE name or term
- When the AE first occurred (start date)
- When the AE stopped (stop date), (or an indication of “ongoing”)
- How long the AE persisted (optional)
- Severity of the AE
- Seriousness
- Actions taken
- Outcome
- Investigator opinion regarding the relationship of AE to the study drug(s)

13.7 FOLLOW UP OF PATIENTS WITH ADVERSE EVENTS

The Investigator will follow patients with AEs, even if the patient was withdrawn from the study due to the AE, until the adverse event has:

- resolved
- the patient has returned to baseline state of health,
- the patient is lost to follow-up,
- the event is otherwise explained,
- the Investigator does not expect any further improvement or worsening of the adverse event.

Medically significant AEs considered related to the investigational product by the investigator or the sponsor will be followed until resolved or considered stable.

14 DATA COLLECTION AND MANAGMENT

Electronic and hard copy CRF's will be provided for the recording of data. With the exception of hard copy case report forms utilized for expedited reporting requirements, such as the reporting of SAE's, the remainder of patient data will be collected and submitted via electronic CRFs. All data should be substantiated by clinical source documents organized within a patient research record. ICH Good Clinical Practices are to be followed.

Electronic data for on study and follow-up patient data is submitted via the electronic system called REDCap (Research Electronic Data Capture). REDCap is managed from the Medical University of South Carolina as a consortium partner under their CTSA. REDCap CRF is a secure, Web-based application designed to capture and manage research study data.

The system has been reviewed for 21CFR Part 11 compliance and has been deemed "21CFR 11 Capable." Users of the REDCap system are limited to members of the IRB approved research team who are delegated data management responsibilities, typically the study coordinator and data manager.

15 ETHICAL AND REGULATORY CONSIDERATIONS

The following must be observed to comply with Food and Drug Administration regulations for the conduct and monitoring of clinical investigations; they also represent sound research practice:

15.1 INFORMED CONSENT

The principles of informed consent are described by Federal Regulatory Guidelines (Federal Register Vol. 46, No. 17, January 27, 1981, part 50) and the Office for Protection from Research Risks Reports: Protection of Human Subjects (Code of Federal Regulations 45 CFR 46). They must be followed to comply with FDA regulations for the conduct and monitoring of clinical investigations.

15.2 INSTITUTIONAL REVIEW

This study must be approved by an appropriate institutional review committee as defined by Federal Regulatory Guidelines (Ref. Federal Register Vol. 46, No. 17, January 27, 1981, part 56) and the Office for Protection from Research Risks Reports: Protection of Human Subjects (Code of Federal Regulations 45 CFR 46)

